## **Objectives**

The objective of this study is to determine if citicoline is effective for balance abnormalities and to stabilize cognitive decline in patients with FXTAS.

# Design and Outcomes

The design of this study is an open label study conducted at one center. The primary outcome is change in the FXTAS Rating Scale (FXTAS-RS). Secondary outcome measures include neuropsychological tests (Behavioral Dyscontrol Scale, Stroop, WAIS PIQ, WASI, Animal Naming, Purdue Pegboard, Digits Backwards, Symbol Digits, and COWAT), instrumented Timed up and go (iTUG) test, Computed Dynamic Posturography (CDP), Activities-specific balance confidence (ABC) scale, Beck Anxiety Inventory (BAI), and Center for Epidemiological Studies Depression Scale Revised (CESD-R).

#### Interventions and Duration

The intervention will be 1000mg of citicoline once daily. Outcome measures and neurological examination will be performed at baseline, 3 months, 6 months, and 12 months.

## Sample size and population

Sample size for the initial pilot study is ten patients. All patients will meet critieria for possible, probable, or definite FXTAS per the Jacquemont et al diagnostic criteria (Jacquemont, 2003). There will be no stratification or randomization.

#### STUDY OBJECTIVES

# Primary Objective

The hypothesis tested is that citicoline will result in improvement of scores on the FXTAS Rating Scale after 12 months of treatment. The null hypothesis is that there will be no difference between baseline and final outcome measures on the FXTAS Rating Scale. This scale will be performed by the principal investigator, a movement disorder neurologist involved in the development of this scale.

Secondary Objectives

There are two secondary hypotheses. First, we hypothesize that subjects will have stabilization of cognitive decline on citicoline. This hypothesis will be tested by measuring scores on the following neuropsychological tests: Behavioral Dyscontrol Scale, Stroop, WAIS PIQ, WASI, Animal Naming, Purdue Pegboard, Digits Backwards, Symbol Digits, and COWAT. Second, we hypothesize that patients will improve on Computed Dynamic Posturography and the instrumented Timed up and go test. The secondary outcomes will be performed by the study team and led by the site investigator.

## BACKGROUND

#### Rationale

Fragile X-associated tremor/ ataxia syndrome (FXTAS) is characterized by tremor, cerebellar ataxia, frequent falls, cognitive decline and progressive loss of motor function. It is a newly recognized, late onset neurodegenerative disorder that occurs in carriers of a premutation in the fragile X mental retardation 1 (*FMR1*) gene located on the X chromosome. There are approximately 785,000 female and 314,000 male *FMR1* premutation carriers in the US and roughly 75% of men and 15% of women carriers will develop FXTAS in their lifetime. There are currently no targeted therapeutic treatments for FXTAS. However, there are promising pharmaceutical treatment approaches with potential symptomatic benefits based on their effectiveness in treating disorders that have significant phenotypic overlap with FXTAS.

Citicoline is an endogenous nucleotide and intermediate in the biosynthesis of structural membrane phospholipids and has been shown in initial studies to be effective in treating neurodegenerative disorders associated with head trauma, stroke, brain aging, cerebrovascular pathology and Alzheimer disease (Alvarez, 1999). FXTAS occurs in some carriers of a premutation size expansion (55-200 CGG repeats) in the promoter region of the *FMR1* gene. Increased CGG repeat length leads to increased *FMR1* mRNA, which is implicated in the neuronal toxicity causing motor and cognitive dysfunction in FXTAS. In a FXTAS *Drosophila* model, citicoline demonstrated the ability to reduce neuronal toxicity caused by CGG repeat *FMR1* mRNA by decreasing locomotion deficits and lethality (Qurashi, 2012). Citicoline also improved cognitive performance in patients with Alzheimer disease and mild dementia when given at 1,000 mg per day (Alvarez, 1999). Currently there are no FDA approved medications for treatment of the motor and cognitive dysfunction in FXTAS patients

The study drug regimen in this protocol is similar to those studies conducted for Alzheimer disease and stroke. The active study drug will be dosed once daily due to convention. There are no aspects of the proposed dosing schedule that are not FDA-approved for other indications. This study is of high priority due to the absence of any proven medications to treat the symptoms of this disorder.

## STUDY DESIGN

This is an open label designed study. Citicoline was chosen because of its novel mechanism of action and its preliminary success in treating some forms of neurological

disease. This will be the first clinical trial testing citicoline in patients with FXTAS. Citicoline has demonstrated the ability to mediate neuronal toxicity presumably via its inhibition of phospholipase A2. This action of phospholipase A2 inhibition may provide a mechanism to mitigate locomotion and cognitive deficits in this patient population.

# SELECTION AND ENROLLMENT OF SUBJECTS

## *Inclusion criteria*:

- Subjects will be diagnosed with Fragile X-associated tremor/ataxia syndrome (FXTAS) by the Jacquemont et al diagnostic criteria (see Table 1).
- Serum creatine kinase, complete metabolic panel, complete blood count, liver function tests, renal function tests, platelets and EKG are within normal limits (results obtained from primary care physician and dated within the past 6 months or obtained at screening visit).
- Older than age 18.

## Exclusion criteria:

- Patient refuses to assent or no LAR if cognitively impaired
- Presence of severe renal disease (BUN 50% greater than normal or creatinine clearance <60 mL/min) or hepatic disease.
- Abnormal creatine kinase and/or platelet count in the past 6 months (as determined by lab reports obtained from primary care physicians or conducted at baseline).
- Women of childbearing potential who are pregnant at the time of screening or who will not use adequate protection during participation of the study.
- Allergy/sensitivity to the citicoline or its formulations.
- Concurrent participation in another clinical study.
- Active substance use or dependence.
- Serious illness (requiring systematic treatment/or hospitalization) until the subject either completes therapy or is clinically stable on therapy, in the opinion of the site investigator, for at least 60 days prior to study entry.

**Table 1:** Diagnostic criteria for FXTAS (adapted from Jacquemont et al., 2003)

Molecular	FMR1 CGG Repeat Size 55-200
Clinical	
Major signs:	Intention tremor
	Gait ataxia
Minor signs:	Parkinsonism
	Moderate to severe short term memory deficits
	Executive function deficits
Radiological	
Major signs:	MRI white matter lesions in the middle cerebellar peduncle (MCP
sign)	
-	

Minor signs: MRI white matter lesions in cerebral white matter

Moderate to severe generalized atrophy

Diagnostic Categories

**Definite:** Presence of one major radiological sign plus one major clinical symptom **Probable:** Presence of either one major radiological sign plus one minor clinical

symptom or

has two major clinical symptoms

**Possible:** Presence of one minor radiological sign plus one major clinical symptom

## Study Enrollment Procedures

Patients with Fragile X-associated tremor/ataxia syndrome (FXTAS) will be recruited through the Parkinson Disease and Movement Disorder clinic at Rush University Medical Center. There are nine movement disorder attending physicians and two fellows who see about 25 FXTAS patients a year as new patients and in follow up. Recruitment goals are expected to be predominantly achieved through the cohort of individuals seen at Rush, but advertising may also be conducted through monthly FXTAS meetings to enhance enrollment. Potential subjects may be identified by their treating physician in the Movement Disorders Clinic at Rush or referred to Rush from elsewhere. If a patient is interested in enrolling in the study, they will be invited to an initial study visit, at which they will sign informed consent after a full explanation of the study.

Documentation of inclusion and exclusion criteria will occur if the patient is interested in enrollment. Eligible subjects who refuse participation will be given the option of later enrollment if they should choose to join the study.

Much of recruitment will occur from physicians with a treatment relationship with the patient. Consent will occur between the primary investigator on the study and the potential subject. All investigators are trained in the conduct of human research. The patient will have a mini mental state examination (MMSE) performed to determine level of understanding prior to the consent process. If the potential subject scores less than 25, the patient will not be allowed to gain entry into the study. A copy of the consent form will be provided to all subjects.

# STUDY INTERVENTIONS

#### Interventions, Administration, and Duration

Ten subjects will receive 1,000mg once daily of citicoline. Each subject will stay on the study drug for 12 months. The outcome measures will be assessed at baseline and then again at the end of month 3, month 6, and month 12. The subjects will continue taking the same study drug at the same dose throughout the entire trial. There are no expected side effects, however, adverse events will be monitored throughout the study. Subjects will be seen and treated in the outpatient Movement Disorders Clinic at Rush. Subjects will come to the clinic for 6 in person visits and 3 telephone visits will be conducted. All patients may remain on other medications for neurologic signs, but the dose of these medications needs to remain stable during the 12 months of the study.

The Handling of Study Interventions

The study drug will be manufactured by Jarrow Formulas and purchased from the online retailer ProVitaminas in the form of 250mg capsules. The study drug will then be shipped to the Principal Investigator at Rush. The study drug will be dispensed by the study team at Rush who will dispense the study drug to the subjects. The study drug will be stored at room temperature in the Parkinson Disease and Movement Disorder clinic which will be secured by lock. The study drug will be provided to the subjects in pill bottles. They will receive four capsules of 250mg daily for the 12 months of intervention. Subjects should take four capsules once a day at mealtime, or two capsules twice a day at mealtime if they are having upset stomach. Subjects will be asked to return any unused study drug after 12 months to Rush. Study intervention accountability records will be completed according to the Manual of Operations.

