#### Concomitant Interventions

Medications for neurological signs of Fragile X-associated tremor/ataxia syndrome need to be stable during the 12 months of this study. There are no contraindicated interventions.

- Required Interventions: citicoline 1,000mg once daily.
- Prohibited Interventions: none.

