#### Baseline

The baseline (entry) visit will occur at least two weeks after the screening visit to allow for adequate study drug supply. Study drugs will be dispensed at the entry visit.

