## • Final Evaluations

The final visit will consist of blood chemistry and hematology, neurological examination, FXTAS Rating Scale, neuropsychological tests, Computed Dynamic Posturography, instrumented Timed up and go test, rating scales, and adherence assessment.

Special Instruction and Definitions of Evaluations

The source document will include all of the following listed below.

- Informed Consent: The patient will have an opportunity to review the consent form and ask any questions prior to signing the form. If the patient has dementia, they will be excluded from the study. Documentation of the consent will be given to the subject, and copies will be maintained in the study chart and the hospital record.
- Documentation of FXTAS: Diagnosis of FXTAS will need to be documented prior to entry in the patient's chart.
- Medical History: The subject's history regarding FXTAS will be obtained or a record of this history secured for the study chart. A complete social history, family history, and review of systems will also be performed.
- Treatment History: Allergies will be reviewed. Prior and current medications and other treatments will be reviewed and documented.
- Clinical Assessments: Clinical assessment procedure will be reviewed at the baseline
  entry visit and neurological examination performed. Clinical assessments to review
  safety, tolerability, and effectiveness will be conducted at each face-to-face visit or
  over the phone. Neurological examination will occur at the face-to-face visits only.
  Change in neurological signs or symptoms, adverse events, or tolerability issues
  should be recorded on the CRFs.
- Laboratory Evaluations: Blood chemistry and hematology will be performed and the resulting laboratory result form placed in the study record.
- Questionnaires and Rating Scales: Scoring for each item on the FXTAS Rating Scale will be recorded in the scoring grid. Scoring for the neuropsychological tests, CDP, iTUG, ABC, BAI, CESDS-R, and MoCA will be recorded in the CRF.
- Adherence Assessments: Pill counts and questionnaires will be filled out at every phone or in person visit.

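### Doses of neurological drugs need be stable only during the study, and recent citicoline use is not excluded, so a change completed just before baseline can slightly disturb the paired comparison

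*Combined protocol and SAP*

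**What the plan says.** The section Interventions, Administration, and Duration lets subjects keep taking other drugs for neurological signs, provided that "the dose of these medications needs to remain stable during the 12 months of the study". Concomitant Interventions repeats the rule: "Medications for neurological signs of Fragile X-associated tremor/ataxia syndrome need to be stable during the 12 months of this study". The same section lists "Prohibited Interventions: none".

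The inclusion and exclusion criteria contain no look-back for these drugs. Citicoline appears there only as an allergy or sensitivity exclusion. The one pre-entry stability window is 60 days, and it concerns serious illness.

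The treatment-history item under Final Evaluations states: "Prior and current medications and other treatments will be reviewed and documented". Table 2 places that history at screening. Under Baseline, "The baseline (entry) visit will occur at least two weeks after the screening visit"; the reason given is drug supply. No eligibility rule uses the recorded history.

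The primary hypothesis is that "citicoline will result in improvement of scores on the FXTAS Rating Scale after 12 months of treatment". Outcome and Data Analysis tests it with a paired t-test on the total FXTAS-RS. There is no control group.

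**The concern.** In a single-arm paired comparison, the baseline score is the only reference. If another drug was changed just before baseline and its effect is still developing, part of the later change in score belongs to that drug, and no comparator removes it. A recent start or increase would look like improvement on citicoline, and a recent stop or reduction like worsening. A subject already taking citicoline at baseline would hide benefit.

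The in-study rule narrows the gap. Someone still titrating at baseline would break it at the next dose step. What escapes is a change already complete at baseline, or a baseline measured on citicoline.

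For the primary test, only displacement that lasts to month 12 counts. The Rationale describes the disease as marked by "tremor, cerebellar ataxia, frequent falls, cognitive decline and progressive loss of motor function", so a short-lived drug effect may be a small part of a 12-month change. At stake is a small avoidable disturbance in an estimate that the protocol intends to use for planning a phase III study.

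**Working it through.** **Inputs from the documents.** n = 10 (Sample size and population). SD of the score 11 and planned mean change -7.3 (Sample Size and Accrual). A lower score is better.

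**The plan's own figure.** The protocol quantifies nothing on this point. The SD and change come from its calculation of 58 patients. That figure is reproduced by two independent groups, one-sided 0.05 and 80% power: 2 × [11 × (1.645 + 0.842) / 7.3]² = 28.1, so 29 per group and 58 in total. Alpha is printed as 0.5. I read it as 0.05. Nothing below depends on the 58.

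**Assumptions, because the documents are silent.**
- Two-sided test at 0.05.
- Baseline-to-final correlation r of 0.5 or 0.8. SD of change = 11 × √(2(1 - r)) = 11.0 or 6.96.
- k subjects affected, each displaced by g points.
- g of 1.825, 3.65 or 7.3, which is 25%, 50% and 100% of the planned change. These are illustrative values; none is a bound.

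**Shift in the mean change** = k × g × (fraction lasting to month 12) / 10.
- k = 1, full persistence: 0.18, 0.37 or 0.73 points.
- k = 2, same direction, full persistence: 0.365, 0.73 or 1.46 points.

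**Against the precision of the trial.** The 95% CI half-width is 2.262 × SD / √10 = 7.87 or 4.98 points. For k = 2 and g up to 3.65, the shift is between 0.365/7.87 = 5% and 0.73/4.98 = 15% of it.

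**Rejection rates with no citicoline effect.** One million simulated paired t-tests per cell, displacing only the affected subjects. Two subjects, both towards improvement, full persistence; cells give improvement / worsening / total, in %:

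| g | SD of change 11.0 | SD of change 6.96 |
|---|---|---|
| 1.825 | 3.05 / 1.98 / 5.03 | 3.43 / 1.71 / 5.14 |
| 3.65 | 3.70 / 1.52 / 5.22 | 4.44 / 1.07 / 5.51 |
| 7.3 | 4.96 / 0.82 / 5.78 | 6.38 / 0.34 / 6.72 |

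Without displacement each tail is 2.5%. The tails swap if the displacement is towards worsening.

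**Variations.**
- One subject affected: total 4.9% to 5.0% in every cell.
- Two subjects, half the displacement lasting: total 5.0% to 5.2% for g up to 3.65, and at most 5.6% for g = 7.3.
- Direction random for each affected subject: total about 5% and each tail about 2.5%, for k = 1 or 2 and g up to 7.3.
- One subject displaced each way: mean shift 0, total below 5% (3.2% at the lowest).

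**Prior citicoline.** One subject already at full effect contributes no change, so the mean shows 9/10 of a true effect, a loss of 10%.

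**The case against.** The strongest reply is that the effect is close to nothing. If the direction of recent changes is unknown, rejection stays at 5% and the result is only noisier. That stands. A bias needs changes in the same direction. Recent treatment starts among clinic patients could produce that, but the documents give no frequency.

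Second, the plan partly covers the matter. It speaks of patients remaining on their drugs, which presupposes an existing regimen, and it records medication history, so an affected subject among ten could probably be identified. That also stands in part, but no duration before baseline is given and the record has no consequence for entry.

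Third, the protocol says that the pilot examines methods and safety and is too small to determine efficacy. This limits the consequence. It still tests an efficacy hypothesis and carries the data forward.

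A reader might infer more than the text supports:
- *That titration may continue through the study.* The in-study rule forbids it.
- *That citicoline users will enrol.* The study drug is "purchased from the online retailer", which shows where the study buys it. Nothing reports earlier use by patients.
- *That subjects will be on L-Dopa.* Management of Adverse Experiences provides for the case without saying that it will occur.
- *That the false-positive rate rises to 6.6% or 9.1%.* Those figures come from shifting all ten subjects by 1.46 points. Displacing two subjects by 7.3 also widens the spread, and gives 5.8% or 6.7%.
- *That 7.3 points is the worst case.* The remark that other treatments lack efficacy explains expected low loss to follow-up. It bounds no displacement on the total scale.

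**Conclusion.** The gap is real and minor. The protocol allows a drug change completed just before baseline, or a baseline measured on citicoline, in an uncontrolled comparison where each subject carries a tenth of the mean.

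Mixed directions mainly add noise. For two subjects displaced the same way by up to 3.65 points, the mean moves by 0.37 to 0.73 points. Total rejection is then about 5.0% to 5.5%, and false improvement 3.1% to 4.4% instead of 2.5%. These figures rest on an assumed two-sided 0.05 test, an SD of change of 7 to 11, full persistence to month 12, and assumed values for the number affected and the displacement. Prior citicoline use is only a possibility.

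The uncontrolled open-label design remains the main limit on interpretation.

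**What to change.** Make three changes:
- Require stable doses of drugs for neurological signs for a fixed period before baseline as well as during the study. Sixty days is a pragmatic example, matching the length already used for serious illness. It is not a derived stabilisation or washout time, and the investigator should set it.
- Exclude citicoline use in the same period, with re-screening allowed.
- Record the date of the last dose change in the treatment history and recheck it at baseline.

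A separate ban on non-study citicoline during treatment adds little, because the regimen already fixes intake at 1,000 mg daily. No extra analysis is needed.

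The cost is two eligibility lines and one date field. Some candidates would wait, only partly within the existing gap of at least two weeks, or would be lost, in a clinic that sees about 25 FXTAS patients a year. The change removes one small source of disturbance. It does not make the observed change attributable to citicoline.

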#### Concomitant Interventions

Medications for neurological signs of Fragile X-associated tremor/ataxia syndrome need to be stable during the 12 months of this study. There are no contraindicated interventions.

- Required Interventions: citicoline 1,000mg once daily.
- Prohibited Interventions: none.

#### Adherence Assessment

Adherence will be assessed by pill counts and adherence questionnaires that will be completed at each of the study visits. Because the study is using an intent to treat analysis, adherence will be reported using descriptive statistics.

## CLINICAL AND LABORATORY EVALUATIONS

## Timing of Evaluations

Subjects will be consented and have initial laboratory studies and rating scales at the baseline visit. Once on the study drug, they will be contacted by phone at Week 3 for questions regarding side effects, clinical issues, and to answer any questions. The subjects will be reassessed after six weeks for anxiety and depression, and they will continue with the intervention. Again, they will be contacted by phone at Week 9 and Month 9 to assess for safety and tolerability. They will be seen in the clinic at Month 3, Month 6 and Month 12and outcome measures will be performed.

Table 2

Evaluation	Screening	Baseline	Week	Week	Week	Month	Month	Month	Month
			3/TC	6	9/TC	3	6	9/TC	12
	Visit 1	Visit 2	Visit 3	Visit 4	Visit 5	Visit 6	Visit 7	Visit 8	Visit 9
			/TC		/TC			/TC	
Informed Consent	X								
Documentation of	X								
FXTAS									
Medical/Treatment	X								
Hx									
Clinical Assessment		X		X		X	X		X
Neurological Exam		X		X		X	X		X

Adherence			X	X	X	X	X	X	X
Assessments									
Questionnaires		X				X	X		X
FXTAS-RS and		X				X	X		X
other rating scales									
Beck Anxiety/		X				X	X		X
CESDS-R scales									
Mini Mental State	X								
Exam (MMSE)_									
Neuropsychological		X				X	X		X
battery of tests									
Computed		X				X	X		X
Posturography/iTUG									
EKG		X							
Lab tests	X					X	X		X
Safety and					X			X	
tolerability phone									
call									

